### 6.7.2. Mortality

For analysis of the time to death or mortality, the Kaplan-Meier method will be used. The times between surgery and the most recent or last available assessment per subject will be used together with the times between surgery and the date of death. This analysis is part of the final report.

Evaluation Variable / Question	Level of Measurement	Recode and Analysis Plan
All Assessments - Mortality		
Creation of variable Difference between Date of Surgery [dd.mm.yyyy] and Date of Death [dd.mm.yyyy] in [ ] days [ ] (Variable(s): VISITDT; DOSEDD)	Quantitative, ratio	
Case summary with number and percentage of valid cases/values, missing cases/values (if any) and total cases/values.
 
Mean, median, interquartile range, maximum, minimum, standard deviation, 95% confidence interval for mean, Shapiro-Wilk Test.

Creation of variable Difference between Date of Surgery [dd.mm.yyyy] and Date of “most recent” Visit [dd.mm.yyyy] in [ ] days [ ] (Variable(s): VISITDT)	Quantitative, ratio	N/A (Analyzed above), used for survivorship
Create new variable “Grouping variable - Mortality” (Variable(s): PRIMRSN)	Qualitative, nominal	
 
- censored = survivors
 
- events = death
 

Create new variable “Combined Time - Mortality” (Variable(s): VISITDT; DOSEDD)	Quantitative, ratio	
 
- Use time between surgery and most recent visit for surviving subjects
 
- Use time between surgery and death for deceased subject
 

Use variables “Combined Time - Mortality” and “Grouping variable - Mortality”	Qualitative, nominal Quantitative, ratio	
Case summary with number and percentage of valid cases/values, missing cases/values (if any) and total cases/values.
 
Kaplan-Meier survival analysis: subject ID, time, status, cumulative proportion, Kaplan-Meier estimate, standard error of KM estimate, number of cumulative events, number of remaining cases, mean for survival time with 95% confidence interval, survival graph, hazard graph.

Table 6.7.2.1: All Assessments – Mortality Tables List

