10.4. SCHEDULE OF EVENTS

Assessment	Pre-Operative	Operative/ Discharge	6 Weeks ^{a, b} (+/- 2 weeks)	6 Months ^{a, b} (+/- 3 weeks)	12 Months ^{a, b} (+/- 4 weeks)	24 Months ^{a, b} (+/- 4 weeks)	Annually ^b
Informed Consent	X						
Demographics & Medical History	X						
Inclusion/Exclusion	X						
Physical Exam	X		X ^c	X ^c	X ^c	X ^c	X ^c
Surgical Procedure		X					
ASES Shoulder Score	X		X ^d	X ^d	X ^d	X ^d	X ^d
Image Evaluation ^{e, f}	X	X	X	X	X	X	X
Subject Disposition ^g			X	X	X	X	X
	Device-Related AEs/Incidents & Reoperations will be collected throughout the course of the clinical investigation.						

	
a. Follow-up visit schedule to reflect Institutions' Standard of Care practicesb. If the subject misses a visit and is outside of the visit window, then every effort should be made to collect data instead of noting visit as missed.c. Evaluation may be collected when subject presents in-clinic for study visit.d. Evaluation can be collected via phone.e. Radiograph collection should follow Institution's Standard of Care practices and no additional x-rays should be made for study purposes.f. CT scans may be collected if part of Institution's Standard of Care practices.g. Subject Disposition assessment will occur at any time point for subject withdrawal prior to the completion of the clinical investigation.
--	-----------------------------------------------------------------------------------------------------------------------------------------------------------------------------------------------------------------------------------------------------------------------------------------------------------------------------------------------------------------------------------------------------------------------------------------------------------------------------------------------------------------------------------------------------------------------------------------------------------------------------------------------------------------------------------------------------------------------------------------------------------------------------------------------------------------------------------------------

Table 1: Schedule of Events

11. Statistical Methods

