11.3.3. Secondary Endpoints

The incidence of device-related AEs and implant survivorship will be assessed up to 10 years after the index procedure and monitored through collection and analyses. These analyses will be part of the annual and final reports.

Furthermore, time to (earliest) device-related AEs will be analyzed as well. For analysis of the time to the (earliest) device-related AEs as well as the time to secondary procedure (revision, removal, reoperation), the Kaplan-Meier method will be used. The time between surgery and the last available assessment will be used together with the time between date of surgery and the date of secondary procedure. Considered variables, the level of measurement and the planned analysis steps are listed in detail in the SAP.

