11.3.4. Additional Analyses

Additional analyses are outlined in the subsequent sections. Analysis details (variables, level of measurement, planned steps) are listed in-depth in the SAP.

- **Mortality**

For analysis of the time to death or mortality, the Kaplan-Meier method will be used. The times between surgery and the last available assessment will be used together with the times between date of surgery and the date of death. This analysis will be part of the annual and final reports.

- **Total ASES Shoulder Score – Within subject changes by visit**

The within subject score changes of the ASES Shoulder Score from visit to visit will be analyzed to help identify the changes on the subject level. This analysis will be part of the annual and final reports.

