## 6.6. ANALYSIS OF CI ENDPOINTS

Evaluation Variable / Question	Level of Measurement	Analysis Plan					
Endpoints – Primary Endpoint							
Use variable Total ASES Score 24 Months [points]:							
Based on the underlying distribution of the data and the result of the normality assessment, either the parametric one-sample t-test or the non-parametric one-sample sign test will be used to compare the 24 months postoperative ASES Shoulder Score results of the ReUnion RSA group against the lower maximum acceptable difference ( $-\theta$ ) of 51.87 points.							
The analysis of the primary endpoint will be part of the final report.							

Table 6.6.1: Endpoints – Primary Endpoint Tables List

Evaluation Variable / Question	Level of Measurement	Recode and Analysis Plan	Inclusion		
Adverse Events – Time to (earliest) Device-Related Adverse Event / Incident			IR	FR	N/A
Creation of variable Difference between Date of Surgery [dd.mm.yyyy] and Date of First Device Related Adverse Event [dd.mm.yyyy] in [ ] days [ ] (Variable(s): VISITDT; AEONSTD)	Quantitative, ratio	Case summary with number and percentage of valid cases/values, missing cases/values (if any) and total cases/values. Mean, median, interquartile range, maximum, minimum, standard deviation, 95% confidence interval for mean, Shapiro-Wilk Test.		X	
Creation of variable Difference between Date of Surgery [dd.mm.yyyy] and Date of “most recent” Visit [dd.mm.yyyy] in [ ] days [ ] (Variable(s): VISITDT)	Quantitative, ratio	N/A (Analyzed above), used for survivorship		X	
Create new variable “Grouping variable – First Device Related Adverse Event” (Variable(s): AEONSTD)	Qualitative, nominal	- censored = survivors - events = first (earliest) Device Related Adverse Event		X	

Create new variable “Combined Time – First Device Related Adverse Event” (Variable(s): AEONSTDT)	Quantitative, ratio	- Use time between surgery and “most recent” visit for surviving subjects - Use time between surgery and first device related adverse event for subjects with device related adverse event	X	

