### 6.7.3. Reoperation Surgery

For analysis of the time to the reoperation, the Kaplan-Meier method will be used. The times between surgery and the most recent or last available assessment per subject will be used

together with the times between surgery and the date of reoperation (earliest reoperation in case that one subject experienced more than one reoperation). This analysis is part of the final report.

Evaluation Variable / Question	Level of Measurement	Recode and Analysis Plan
Adverse Events / Reoperation Surgery		
Creation of variable Difference between Date of Surgery [dd.mm.yyyy] and Date of First Reoperation [dd.mm.yyyy] in [ ] days [ ] (Variable(s): VISITDT)	Quantitative, ratio	Case summary with number and percentage of valid cases/values, missing cases/values (if any) and total cases/values. Mean, median, interquartile range, maximum, minimum, standard deviation, 95% confidence interval for mean, Shapiro-Wilk Test.
Creation of variable Difference between Date of Surgery [dd.mm.yyyy] and Date of “most recent” Visit [dd.mm.yyyy] in [ ] days [ ] (Variable(s): VISITDT)	Quantitative, ratio	N/A (Analyzed above), used for survivorship
Create new variable “Grouping variable – First Reoperation” (Variable(s): VISITDT)	Qualitative, nominal	- censored = survivors - events = first (earliest) Reoperation
Create new variable “Combined Time – First Reoperation” (Variable(s): VISITDT)	Quantitative, ratio	- Use time between surgery and most recent visit for surviving subjects - Use time between surgery and first reoperation for subjects with reoperation(s)
Use variables “Combined Time – First Reoperation” and “Grouping variable – First Reoperation”	Qualitative, nominal Quantitative, ratio	Case summary with number and percentage of valid cases/values, missing cases/values (if any) and total cases/values. Kaplan-Meier survival analysis: subject ID, time, status, cumulative proportion, Kaplan-Meier estimate, standard error of KM estimate, number of cumulative events, number of remaining cases, mean for survival time with 95% confidence interval, survival graph, hazard graph.

Table 6.7.3.1: All Assessments – Reoperation Surgery Tables List

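### The three Kaplan-Meier analyses date events exactly but stop event-free subjects at their last visit, which biases event estimates upward: severely in the tail of any annual-report curve, slightly in the final report

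*SAP*

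**What the plan says.** **Time rule.** In SAP 6.7.2 (Table 6.7.2.1) the time variable for survivors is defined by "Use time between surgery and most recent visit for surviving subjects" and for deaths by "Use time between surgery and death for deceased subject". SAP 6.6 (Table 6.6.2) follows the same pattern: event-free subjects stop at the most recent visit, and for the others "Use time between surgery and first device related adverse event for subjects with device related adverse event". SAP 6.7.3 (Table 6.7.3.1) pairs the most recent visit with the time to first reoperation. The protocol has the same construction in 11.3.4 for death ("The times between surgery and the last available assessment will be used together with the times between date of surgery and the date of death") and in 11.3.3 for secondary procedures.

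**Collection.** Protocol 10.4 states: "Device-Related AEs/Incidents & Reoperations will be collected throughout the course of the clinical investigation". From 12 months on, scheduled visits are a year apart.

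**What is absent.** Neither document carries an event-free subject forward to a data cut, a withdrawal date or a last contact. Neither limits events to those before some common end.

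**Which reports.** Protocol 11.3.4 places mortality in the annual and final reports. Protocol 11.3.3 says this of AE incidence and survivorship, and introduces the time-to-event curves in the next paragraph. SAP 3.1.2, 3.1.3, 6.7.2 and 6.7.3 place the curves in the final report.

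**The concern.** Kaplan-Meier estimation needs the end of a subject's observation to be independent of whether the event happened. Here it is not. If a subject was last seen at month 24 and dies at month 30, the six months after the visit count. If the same subject is alive at month 30, they do not. Event-free time is removed from the denominator while events from the same stretch of time stay in the numerator, so the bias can only be upward.

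Death always falls after the subject's last visit, so every death is exposed to the rule. AEs and reoperations are exposed only when they occur after the subject's most recent visit at the time of analysis.

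AE incidence and implant survivorship are the plan's named secondary endpoints. An interim curve that drops steeply at its right-hand end could be read as a device signal when it comes from the censoring rule.

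**Working it through.** The documents give no event rate or survival figure, so there is no stated number to reproduce.

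**Inputs from the documents.** 80 subjects; accrual over 12 months; visits at 6 weeks, 6, 12 and 24 months with the stated windows, then yearly to 10 years; overall dropout 56%; data freeze for the final report after all final assessments (Protocol 19).

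**Assumptions.** Constant event rate of 1 to 5% per year; uniform accrual; a window of ±4 weeks for the annual visits; exponential dropout reaching 56% at 10 years where dropout is included.

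**Step 1: the mechanism by hand.** Each event multiplies the survival estimate by 1 − 1/n, where n is the number at risk. Suppose every event-free subject was last seen at about month 24 and one subject dies at month 30. Then n = 1, the factor is 1 − 1/1 = 0, and estimated survival is 0%.

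Now take a cut 3 years after first surgery. Subjects have between 24 and 36 months since surgery, so about half, 40 of 80, have passed month 30. With a common end, the factor is about 1 − 1/40 = 97.5%. Under the plan's rule, the only event-free subjects at risk at month 30 are those whose 36-month visit already took place early in its window. Only subjects enrolled in the first 4 weeks can have done so, with an average probability of 1/4: 80 × 4/52 × 1/4 ≈ 1.5 subjects. In simulation at 2% per year the mean number at risk at month 30 was 1.6 under the plan's rule and 38 with a common end.

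**Step 2: annual report.** Simulation, 3,000 trials per row, no dropout, incidence at the end of the curve:

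| Cut | Rate/year | Plan's rule | Common end | Trials ending below 50% survival |
|---|---|---|---|---|
| 3 years | 1% | 18% | 3% | 16% |
| 3 years | 2% | 31% | 6% | 31% |
| 3 years | 4% | 50% | 11% | 55% |
| 4 years | 2% | 32% | 8% | 31% |

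True 3-year incidence is 1 − exp(−3 × rate) = 3.0, 5.8 and 11.3%, so the common end recovers it. Adding 56% dropout at 3 years and 2% per year gives 30% against 5.7%, so the result does not depend on full retention.

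**Step 3: the same curves before the tail.** At the 3-year cut and 2% per year, the plan's rule gives 2.0% at 1 year (true 2.0%) and 3.8% at 1.9 years (true 3.7%). At the 4-year cut, the 2.9-year value is 5.7% (true 5.6%). The damage lies beyond the last visit that all subjects have reached.

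**Step 4: final report, 10-year incidence, 56% dropout.**

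| Rate/year | True | Plan's rule, events before withdrawal only | Excess | Events up to 1 year after dropout also counted | All later events counted |
|---|---|---|---|---|---|
| 1% | 9.5% | 9.9% | 0.4 | 10.7% | 14.6% |
| 3% | 25.9% | 26.6% | 0.7 | 28.4% | 36.7% |
| 5% | 39.3% | 40.8% | 1.5 | 42.5% | 52.5% |

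The median number at risk at an event is about 50, and essentially no event meets a risk set of 5 or fewer. Without dropout the two rules agree.

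**The case against.** **The SAP assigns these curves to the final report.** This stands as a limit. The severe figures apply only if annual reports carry the curves. Protocol 11.3.4 requires that for mortality, and 11.3.3 suggests it less directly for AEs and reoperations. Neither document says which prevails, so the exposure is conditional but real.

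**A reader might infer that late events generally fall in a nearly empty risk set, in the final report too.** The documents do not support this. The final report follows all final assessments, so retained subjects stay at risk to year 10. At 2% per year the excess is about 0.6 points (18.8 against 18.1%), against a between-trial standard deviation of about 5 points.

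**A thin tail is visible.** The SAP output includes the standard error and the number of remaining cases. A careful reader would see the problem, but the estimate and the graph would still be wrong.

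**Some inputs fit loosely.** The continuous-collection statement names AEs and reoperations, not deaths. Many listed AEs are perioperative or found on scheduled imaging, and so precede a later visit. Mortality status is taken from the disposition form ("Variable(s): PRIMRSN"), which probably limits the counting of deaths after withdrawal for another reason. The disposition form may itself count as a last assessment, which would narrow the dropout gap. Table 6.7.3.1 lists only the visit date as its source variable, although the text of 6.7.3 refers to the date of reoperation. These points reduce the size for particular curves; they do not make the rule consistent.

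**Nothing is decided on these curves.** True: they carry no hypothesis, and SAP 4.2 sets no stopping rules. That limits the consequence to how safety and survivorship are reported.

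**Conclusion.** The rule is wrong as written in all three analyses, and the direction of bias is upward whatever the event rate. Its importance depends on the report. In an annual report, the end-of-curve incidence at a 3-year cut averages about five to six times the value with a common end at 1 and 2% per year, and more than four times at 4%, while earlier parts of the curve are sound. In the final report the excess is about 0.4 to 1.5 points under 56% dropout when only events before withdrawal count. It grows to about 5 to 13 points if all later events are counted (14.6 − 9.5 = 5.1; 52.5 − 39.3 = 13.2), which the SAP does not clearly exclude for AEs and reoperations.

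The sizes rest on assumed constant event rates, the assumed annual visit window and the assumed dropout pattern. It would go too far to call the curves unreliable throughout, or to say that annual reports will certainly contain all of them.

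**What to change.** In SAP Tables 6.6.2, 6.7.2.1 and 6.7.3.1, and in Protocol 11.3.3 and 11.3.4, define one end of observation per subject and apply it to events and censoring alike. Censor event-free subjects at the date last known event-free: the data cut for subjects still in follow-up, otherwise withdrawal or last contact. Count only events up to that same end. In simulation this removes the bias in both annual and final reports.

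Do not instead count only events on or before the subject's own last visit. A death always falls after that visit, so the mortality curve would lose every death, and no later report would restore it.

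Reconcile Protocol 11.3.3 and 11.3.4 with SAP 3.1.2, 3.1.3, 6.7.2 and 6.7.3 on which reports carry the curves. Name the reoperation date as a source variable in Table 6.7.3.1.

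Cost: one extra date variable (data cut or last contact), minor programming and a wording change in both documents. No new visits are needed.

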### 6.7.3. Reoperation Surgery

For analysis of the time to the reoperation, the Kaplan-Meier method will be used. The times between surgery and the most recent or last available assessment per subject will be used

together with the times between surgery and the date of reoperation (earliest reoperation in case that one subject experienced more than one reoperation). This analysis is part of the final report.

Evaluation Variable / Question	Level of Measurement	Recode and Analysis Plan
Adverse Events / Reoperation Surgery		
Creation of variable Difference between Date of Surgery [dd.mm.yyyy] and Date of First Reoperation [dd.mm.yyyy] in [ ] days [ ] (Variable(s): VISITDT)	Quantitative, ratio	Case summary with number and percentage of valid cases/values, missing cases/values (if any) and total cases/values. Mean, median, interquartile range, maximum, minimum, standard deviation, 95% confidence interval for mean, Shapiro-Wilk Test.
Creation of variable Difference between Date of Surgery [dd.mm.yyyy] and Date of “most recent” Visit [dd.mm.yyyy] in [ ] days [ ] (Variable(s): VISITDT)	Quantitative, ratio	N/A (Analyzed above), used for survivorship
Create new variable “Grouping variable – First Reoperation” (Variable(s): VISITDT)	Qualitative, nominal	- censored = survivors - events = first (earliest) Reoperation
Create new variable “Combined Time – First Reoperation” (Variable(s): VISITDT)	Quantitative, ratio	- Use time between surgery and most recent visit for surviving subjects - Use time between surgery and first reoperation for subjects with reoperation(s)
Use variables “Combined Time – First Reoperation” and “Grouping variable – First Reoperation”	Qualitative, nominal Quantitative, ratio	Case summary with number and percentage of valid cases/values, missing cases/values (if any) and total cases/values. Kaplan-Meier survival analysis: subject ID, time, status, cumulative proportion, Kaplan-Meier estimate, standard error of KM estimate, number of cumulative events, number of remaining cases, mean for survival time with 95% confidence interval, survival graph, hazard graph.

Table 6.7.3.1: All Assessments – Reoperation Surgery Tables List

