8.2. SECONDARY ENDPOINT

In addition to the principal endpoint, information on the following outcomes will be assessed up to 10 years after the index procedure:

Safety: Incidence of device-related intra-operative and post-operative AEs

Efficacy/Performance: Implant survivorship will be monitored

9. Selection of Clinical Investigation Population

Subjects participating in this clinical investigation will be recruited from the investigator's standard subject population, where all patients presenting for primary or revision total shoulder replacement will be evaluated for clinical investigation participation based on the eligibility criteria listed below.

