### 3.1.2. Secondary Analyses

The incidence of device-related AEs and implant survivorship will be assessed up to 10 years after the index procedure and monitored through collection and analyses.

Furthermore, time to (earliest) device-related AEs will be analyzed as well. For analysis of the time to the (earliest) device-related AEs as well as the time to secondary procedure (revision, removal, reoperation), the Kaplan-Meier method will be used. Considered variables, the level of measurement and the planned analysis steps are listed in detail in the SAP. These analyses will be part of the final report.

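### The SAP does not say how an event-free death is handled in the 10-year Kaplan-Meier curves for device-related AEs and reoperation; read as incidence, their complement would run high

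*SAP*

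**What the plan says.** Protocol 8.2 makes "Incidence of device-related intra-operative and post-operative AEs" a secondary endpoint, next to implant survivorship. SAP 3.1.2 sets the horizon: "The incidence of device-related AEs and implant survivorship will be assessed up to 10 years after the index procedure". For time to first device-related AE and "time to secondary procedure (revision, removal, reoperation), the Kaplan-Meier method will be used". Neither document names another time-to-event method.

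Status in the AE analysis (SAP 6.6, Table 6.6.2) has two levels, "censored = survivors" and "events = first (earliest) Device Related Adverse Event". The time for a subject without the event is set by "Use time between surgery and “most recent” visit for surviving subjects". The reoperation analysis (SAP 6.7.3, Table 6.7.3.1) has the same structure, with "events = first (earliest) Reoperation" and "Use time between surgery and most recent visit for surviving subjects".

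Death appears elsewhere:
- SAP 6.7.2 has a separate mortality curve. It uses the date of death and has its own time rule for deceased subjects.
- Protocol 9.3 says a death is not a device failure unless the device caused it or it is attributable to the device. Data up to death enter the final analysis.

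Separately from the curves, SAP 6.1 tabulates device-related AEs and reoperations as frequencies and proportions.

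**The concern.** A subject who has died can no longer have an AE or a reoperation. If the death is censored, Kaplan-Meier treats that subject as still able to have the event later, at the same rate as those under observation. The complement of the curve then estimates what would happen if nobody died, which is higher than the proportion of patients who actually have the event.

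The plan foresees deaths: death is a listed withdrawal reason and has its own curve. Over 10 years the difference could matter to anyone who reads the curves as the AE or reoperation incidence named in the secondary endpoint. Because the AE and reoperation tables lack the row for deceased subjects that the mortality table has, the analyst must also choose a rule that the SAP does not state.

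**Working it through.** **What the coding allows.** A subject dies without a prior device-related AE or reoperation, and the death is unrelated to the device.
1. Under Protocol 9.3 the death is not a device failure, so it is not an event. With two states, it can only be censored, at the last visit. The lead text of SAP 6.7.3, which uses each subject's last available assessment, fits this reading.
2. If *survivors* means alive, the subject has neither a status nor a time and drops out. This conflicts with Protocol 9.3, which keeps data up to death.

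**Inputs.** The plan gives no expected AE, reoperation or death rate, so it has no figure to reproduce here. Assumed: constant event hazard h = 0.01 per year, death hazard d = 0.02 to 0.05 per year, independent of each other, complete follow-up to 10 years.

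**Formulas at 10 years.**
- Deaths censored: 1 − KM = 1 − exp(−10h)
- Cumulative incidence: CIF = h/(h+d) × [1 − exp(−10(h+d))]
- Event-free deaths dropped: CIF / [CIF + exp(−10(h+d))]

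**Results.**
- 1 − KM = 1 − exp(−0.10) = 0.0952
- d = 0.02: CIF = (1/3)(1 − exp(−0.30)) = 0.0864; ratio 0.0952/0.0864 = 1.10
- d = 0.03: CIF = (1/4)(1 − exp(−0.40)) = 0.0824; ratio 1.15
- d = 0.05: CIF = (1/6)(1 − exp(−0.60)) = 0.0752; ratio 1.27
- Deaths dropped: 0.0864/(0.0864 + 0.7408) = 0.104 at d = 0.02; 0.0752/(0.0752 + 0.5488) = 0.121 at d = 0.05

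The gap from censoring is 0.9 to 2.0 percentage points. Dropping the deaths gives a larger one.

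**Early events.** Keep the cumulative event hazard at 0.10 but put 70% of it in the first 2 years, so the hazard is 0.035 per year, then 0.00375. 1 − KM stays at 0.0952.
- d = 0.02: CIF = (0.035/0.055)(1 − exp(−0.11)) + exp(−0.11)(0.00375/0.02375)(1 − exp(−0.19)) = 0.0663 + 0.0245 = 0.0908
- d = 0.05: CIF = (0.035/0.085)(1 − exp(−0.17)) + exp(−0.17)(0.00375/0.05375)(1 − exp(−0.43)) = 0.0644 + 0.0206 = 0.0849

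The gap falls to 0.4 to 1.0 points.

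**Wider range.** With a 10-year net event risk of 5% to 30% and 10-year mortality of 10% to 40%, the ratio is 1.05 to 1.27 (0.3 to 6.2 points) under constant hazards. With 70% of the event hazard in the first 2 years it is 1.02 to 1.13 (0.1 to 3.1 points).

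**Crude proportions.** Simulated trials of 80 subjects, censored at the last scheduled visit, with net event risk 10%:
- 20% mortality and no other loss: 1 − KM 10.1%, Aalen-Johansen 9.0%, crude 9.0%.
- 30% mortality plus 37% loss: 1 − KM 10.2%, Aalen-Johansen 8.3%, crude 6.8%. These rates were chosen to match the plan's 56% drop-out (1 − 0.70 × 0.63 = 0.56); the documents do not split that figure into death and loss.

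So the crude proportion is right when deaths are the only loss, and low once subjects leave alive.

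**The case against.** A reader might infer that the AE incidence the study reports is overstated. The documents do not support that. SAP 6.1 tabulates AEs and reoperations as crude proportions, which do not come from the curves and, with loss to follow-up, err the other way. Nor does the SAP say that one minus Kaplan-Meier will be reported as incidence: the planned outputs are survival estimates and graphs, and the time variable is marked for survivorship.

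A reader might also infer that the SAP prescribes censoring of deaths, or that Kaplan-Meier is invalid here. It does not state the first; censoring follows from the two-state coding and Protocol 9.3. As for the second, censoring unrelated deaths is a legitimate way to estimate net implant survival if death is independent of the event, and implant survivorship is a stated secondary endpoint.

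The size is also open to challenge. The rates are assumed, and many of the foreseeable events in Protocol 13.5 are perioperative, which favours the smaller gap. With 80 subjects fully followed, an estimate of 9.5% has a standard error of √(0.0952 × 0.9048/80) = 3.3 points, or about ±6.4 points at 95%; the illustrated 0.9 to 2.0 points lies well inside that. No test, comparator or stopping rule depends on these curves, and SAP 6.7.3 is filed under additional analysis.

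All of this stands and limits the point. What remains is that the death rule is unstated and that, once subjects are lost, neither planned output estimates the 10-year proportion of patients with an event: the curve's complement runs high and the crude proportion runs low.

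**Conclusion.** The point holds as a gap in the specification with a known direction. The handling of event-free death in Tables 6.6.2 and 6.7.3.1 is unstated. Under either available reading, the complement of the curve exceeds patient cumulative incidence whenever subjects die event-free.

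The illustrated size, 9.5% against 8.6% to 7.5% at 10 years, rests on assumed constant, independent hazards of 1% per year for the event and 2% to 5% for death. It roughly halves if most events come early. The true size cannot be derived from the documents. The change is worth making because it is cheap and supplies a proper estimator for the incidence endpoint; the primary conclusion is not at risk.

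**What to change.** In SAP Tables 6.6.2 and 6.7.3.1:
- Replace the two-level status with three: event, death without prior event, and censored. Date the second by the recorded date of death, already a variable in Table 6.7.2.1, and the third by the last visit.
- Report the Aalen-Johansen cumulative incidence, with 95% confidence intervals at 2, 5 and 10 years, as the incidence estimate.
- Keep the Kaplan-Meier curve with event-free deaths censored, state that rule, and label it net (implant) survival so that it stays comparable with published implant-survival figures.
- Note beside the SAP 6.1 proportions that they are crude and not adjusted for incomplete follow-up.

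The cost is SAP wording and one more estimate per table, from dates already collected. It may need a procedure outside the SPSS Kaplan-Meier menu. Intervals at 10 years will be wide: 56% drop-out would leave about 80 × 0.44 = 35 subjects. No visit, sample size or primary analysis changes.
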